10 CHANGE FROM THE PROTOCOL

Geometric CV% will be calculated as a summary statistic for PK parameters instead of 95% CI of geometric mean, and also CV% is added.

90% CI of geometric LS means of PK parameters will not be calculated. The ratio of geometric LS means will be accompanied by 90% CI.

Summary for laboratory tests will be performed not by treatment but by group because there is no baseline for laboratory tests in Period II.

INR and prothrombin activity are added to coagulation test because these results are reported from the laboratory. Whereas hCG is excluded from urinalysis because the results are not collected.

11 SOFTWARE

All statistical analyses will be performed using SAS version 9.4 or higher.

The PK parameters will be calculated using WinNonlin® software (version 6.3 or later).

APPENDIX 1 PHARMACOKINETIC PARAMETER CALCULATIONS

PK Parameter Calculations		
Parameters	Unit	Calculation
AUC _{0-t}	ng·h/mL	
AUC will be calculated using the linear trapezoidal method and actual times
 $AUC_{t_0-t_n} = \sum_{i=1}^{t_n} \frac{t_i - t_{i-1}}{2} (C_{i-1} + C_i)$ 
AUC_{0-t} will be calculated as AUC when t₀ is set to time zero and t_n is set to t (the last quantifiable concentration time point).

AUC _{0-∞}	ng·h/mL	$AUC_{0-\infty} = AUC_{0-t} + C_{last} / k_{el}$ 
C_{last}: last measurable concentration

AUC% _{ex} *	%	$AUC\%_{ex} = (AUC_{0-\infty} - AUC_{0-t}) / AUC_{0-\infty} \times 100$
AUC ₀₋₂₄	ng·h/mL	will be calculated using time until 24 h drug concentration
C _{max}	ng/mL	will be determined by visual inspection
t _{max}	h	Measured time of C _{max}
t _{1/2}	h	t _{1/2} will be determined as: $t_{1/2} = \log_2 (2) / k_{el}$
k _{el}	1/h	
The exponential rate constant of the terminal phase, k_{el}, will be estimated by log-linear regression, if determinable. The number of data points included in the regression will be determined by visual inspection. Wherever possible, a minimum of 3 data points will be used in the estimation of k_{el}.
 
During the analysis, this calculation method repeats regressions using the last three points with non-zero concentrations, then the last four points, last five, etc. The time of maximum concentration (t_{max}) will be excluded from the estimation of k_{el}. Points with a value of zero for the dependent variable are excluded. For each regression, an adjusted R² is computed
 $\text{Adjusted } R^2 = 1 - \frac{(1 - R^2) \times (n - 1)}{(n - 2)}$ 
where n is the number of data points in the regression and R² is the square of the correlation coefficient.
 
The regression with the largest adjusted R² is selected to estimate k_{el}, with these caveats:
 
If the adjusted R² does not improve, but is within 0.0001 of the largest adjusted R² value, the regression with the larger number of points is used.
 
k_{el} must be positive, and calculated from at least three data points.

CL/F	L/h	CL/F = Dose / AUC _{0-∞}
MRT	h	$MRT = AUMC_{0-\infty} / AUC_{0-\infty}$ 
AUMC_{0-∞}: area under the first moment curve extrapolated to infinity

PK Parameter Calculations		
Parameters	Unit	Calculation
V_z/F	L	$V_z/F = CL/F \times \frac{1}{k_{el}}$
V_{ss}/F	L	$V_{ss}/F = MRT_{po} \times CL/F$
Adjusted R^2 *	—	Refer to calculation of k_{el} .
Number of k_{el} points*	—	will be determined using number of points used in computing k_{el} . If k_{el} cannot be estimated, zero.
Lower limit of k_{el} *	h	will be determined using lower limit on time to be included in the calculation of k_{el} .
Upper limit of k_{el} *	h	will be determined using upper limit on time to be included in the calculation of k_{el} .

* Supplementary parameters.

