In a phase 1 study (Study MT-1186-J01) of oral edaravone in healthy adult males, 74 subjects (54 in the edaravone group and 20 in the placebo group) received single (Cohort S1 to S7) or 5-day repeated administration (Cohort M1 and M2) of edaravone oral solution or suspension at doses of 30 to 300 mg to examine PK, safety and tolerability. The effects of race and meal on PK after single administration at a dose of 200 mg were also examined.

In PK, after single administration of edaravone oral solution or suspension in the fasting state, the C_{max} was reached 0.3 to 0.4 and 0.4 to 0.8 hours after administration, respectively, followed by biphasic or triphasic excretion, with final phase $t_{1/2}$ of 2.4 to 3.2 and 5.1 to 11.8 hours, respectively. C_{max} and AUC of edaravone increased more than dose proportional manner over a dose range of 30 to 300 mg. Plasma concentrations of sulfate conjugate and glucuronide conjugate, both are edaravone metabolites, reached C_{max} 0.5 to 1.4 hours and 0.5 to 1.1 hours after dose, respectively. They were excreted from plasma, with $t_{1/2}$ of 4.9 to 7.9 hours and 2.8 to 5.9 hours, respectively. Meal-effect examination after administration of 200 mg suspension (200 mg/10 mL 0.1% polyvinyl alcohol solution) showed that when edaravone was administered 30 minutes after a meal, C_{max} and AUC of plasma edaravone decreased

to 18.2% and 39.1% of those when it was administered in the fasting state, respectively. Comparison between plasma concentrations in Caucasian subjects and those in Japanese subjects after administration of 200 mg suspension (200 mg/10 mL) showed that C_{max} and AUC of plasma edaravone in Caucasian subjects were 75% and 79% of those in Japanese subjects, respectively. Repeated administration for 5 days did not cause accumulation in plasma concentration.

In terms of safety, no serious adverse events occurred. A total of 21 adverse events were observed in 74 subjects. Among them, the adverse event assessed as causally related to the administration was headache (1 event) in the edaravone group. The event was mild in severity and rapidly resolved. One subject in the edaravone group discontinued the study owing to adverse events. In the meal-effect cohort, moderate conjunctivitis occurred after administration of Cohort S3-1 (200 mg, a single dose in the fasting state), and administration of S3-2 (30 minutes after meal) was called off. This event was considered not related to the investigational product.

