C _{max}	ng/mL	Maximum plasma concentration after administration
CL/F	L/h	Apparent total clearance
k _{el}	1/h	Elimination rate constant from the central compartment
MRT	h	Mean residence time
t _{1/2}	h	Terminal elimination half-life in plasma concentration-time course
t _{max}	h	Time of C _{max}
V _{ss/F}	L	Apparent volume of distribution at steady state
V _{z/F}	L	Apparent volume of distribution during terminal phase

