8.3.2 Pharmacokinetic Parameters

The PK parameters listed in Section 2.1.2 will be calculated for each subject using non-compartmental model. Calculations of the parameters, including supplementary parameters, are described in Appendix 1.

The PK parameters will be summarized by treatment and listed. The supplementary parameters will not be summarized but will be included in listing.

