8.3.3 Analysis of Variance

AUC_{0-t} , $AUC_{0-\infty}$ and C_{max} of unchanged edaravone will be log transformed and analysed. Only subjects with the parameter value under both treatments will be analysed. Analysis of variance (ANOVA) will be used for analysis. Group, treatment, period and subject (nested in group) will be set to factors. Least squares (LS) means for each treatment will be calculated. These values will be back-transformed and shown in table. The difference of LS means between treatments (nasogastric administration minus oral administration) and 90% CI will be calculated. These values will be back-transformed, so that they show the ratio and 90% CI of PK parameters for nasogastric administration compared to oral administration.

As reference, the other pharmacokinetic parameters of unchanged edaravone will be analysed in the same way, although t_{max} will not be log transformed prior to the analysis.

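### As its text reads, the half-life row of SAP Appendix 1 gives the mean lifetime 1/k_el, not ln(2)/k_el: a minor correction, once the logarithm's base is confirmed on the original page

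*SAP*

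**What the plan says.** The SAP's list of PK parameters describes t1/2 as "Terminal elimination half-life in plasma concentration-time course", in hours. Half-life is among the PK parameters in Protocol 5.4.2 and SAP 2.1.2.

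Protocol 10.1 gives no formulas and leaves the calculation methods to the SAP. SAP 8.3.2 then says: "Calculations of the parameters, including supplementary parameters, are described in Appendix 1". Appendix 1 is therefore the only place in either document with a formula for half-life. As the text reads, its relevant rows are:

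- t1/2 = log₂(2) / k_el
- k_el: "The exponential rate constant of the terminal phase", which "will be estimated by log-linear regression, if determinable"; the base of the logarithm is not named
- AUC0-∞ = AUC0-t + C_last / k_el
- Vz/F = CL/F × 1/k_el

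On software, SAP section 11 says: "The PK parameters will be calculated using WinNonlin® software (version 6.3 or later".

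SAP 8.3.3 applies the ANOVA to AUC0-t, AUC0-∞ and Cmax, and adds: "As reference, the other pharmacokinetic parameters of unchanged edaravone will be analysed in the same way". Half-life belongs to that second group.

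**The concern.** The base-2 logarithm of 2 equals 1, so the numerator does nothing and the row reduces to 1/k_el. For exponential decay that is the mean lifetime, not the time in which the concentration halves. The neighbouring rows show that k_el is meant as a natural-base rate constant, so the half-life row looks like a slip in the base of the logarithm.

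Half-life is a listed PK parameter under the secondary objective. It is summarised by treatment and reported with LS means. If someone programmed the row literally, the absolute half-lives would be too long by a constant factor and would not agree with the k_el values listed beside them.

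**Working it through.** **Inputs.** The four Appendix 1 rows above. For illustration only, the terminal half-lives that Protocol section 1 reports from the first oral study (Study MT-1186-J01, 30 to 300 mg), "of 2.4 to 3.2 and 5.1 to 11.8 hours, respectively", for solution and suspension. The documents give no numerical result from the half-life formula, so there is no figure of the plan's own to reproduce.

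**1. Evaluate the formula.** log₂(2) = 1 and ln(2) = 0.6931. For C(t) = C₀·exp(−k_el·t), the concentration halves when exp(−k_el·t) = 0.5, so t = ln(2)/k_el = 0.6931/k_el. The row gives 1.0000/k_el. The ratio is 1/0.6931 = 1.4427, which is 44.3% too long. At t = 1/k_el the fraction remaining is exp(−1) = 36.8%, not 50%.

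**2. Can another base for k_el rescue the row?** Let k be the natural-base constant. The true tail area is C_last/k and the true half-life is ln(2)/k.

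| Log scale of the regression | Slope called k_el | t1/2 row ÷ true half-life | C_last/k_el ÷ true tail area |
|---|---|---|---|
| natural | k | 1.443 | 1.000 |
| base 2 | k/0.6931 | 1.000 | 0.693 |
| base 10 | k/2.3026 | 2.3026/0.6931 = 3.32 | 2.303 |

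No single base makes both the t1/2 row and the AUC0-∞ row right. Only the natural base gives a correct AUC0-∞, and the word exponential in the k_el row also points to it. The half-life row is the one that does not fit.

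**3. Size on the half-life scale (illustration).**

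| Half-life in the earlier study (h) | × 1.4427 (h) |
|---|---|
| 2.4 (solution) | 3.46 |
| 3.2 (solution) | 4.62 |
| 5.1 (suspension) | 7.36 |
| 11.8 (suspension) | 17.02 |

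**4. What is unaffected.** On the log scale the error adds −ln(0.6931) = 0.3665 to every subject's value under both treatments, so it cancels in the NGT-minus-oral difference. With k_el of 0.10 and 0.12 per hour, for example, the half-life ratio is (1/0.10)/(1/0.12) = 1.2, and it is also 1.2 with ln(2) in both numerators. The residual variance does not change, so neither does the 90% CI of the ratio. CV% and geometric CV% do not change either. The formulas for AUC0-t, AUC0-24, AUC0-∞, Cmax, CL/F, MRT, Vz/F and Vss/F do not use t1/2.

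**The case against.** The strongest objection is that the plan may not contain this error. Everything turns on one small subscript in a typeset equation whose text was read from a PDF by machine, and a printed e could have come out as a 2. Hardly anyone would deliberately write the base-2 logarithm of 2, while the base-e form is the ordinary formula. The neighbouring rows, and the natural-log definition of geometric CV% in SAP 6.1, fit authors who had the natural logarithm in mind. This objection stands as a condition. The text alone cannot settle it, and if the original page shows log_e or ln, the point falls away.

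The second objection is about consequence. A reader might infer that every reported half-life will be wrong, or that a check programmed in SAS against Appendix 1 would spread the error. The documents do not support this. Section 11 assigns the PK parameters to WinNonlin and SAS to the statistical analyses, and no section describes half-life being hand-coded or checked in SAS against the appendix. A wrong value would also be easy to spot, because k_el is listed too: t1/2 × k_el would be 1 instead of 0.693. This objection stands and limits the point.

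The third is that half-life does not carry the study's conclusion. It is compared only for reference, and the constant cancels in the comparison. That also stands. None of the three makes the formula right if base 2 is what was printed.

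**Conclusion.** On the text as it reads, the half-life formula is wrong by a factor of 1.443 and is inconsistent with the AUC0-∞ and Vz/F rows of its own table. This assumes that the subscript is a 2 on the original page, and that k_el is a natural-base constant, which the other rows require.

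The reach is small. If the formula were applied literally, individual half-lives, their means, SDs, medians, ranges and geometric means, and the back-transformed LS means for each treatment would be 44% too long. The 5.1 to 7.4 h and 11.8 to 17.0 h shifts only illustrate the scale: they come from an earlier study across 30 to 300 mg and do not predict results at 105 mg. If WinNonlin's own half-life is reported, the effect is limited to a SAP that misstates how the parameter is obtained.

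A reader might infer that the bioavailability comparison is at risk. It is not: AUC0-t, AUC0-∞ and Cmax do not depend on t1/2, and even the half-life ratio and its 90% CI are unchanged. This is a minor correction.

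**What to change.** First look at the t1/2 row on the original page of SAP Appendix 1. If it shows log_e or ln, no change to that formula is needed.

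If it shows base 2, replace the row with t1/2 = ln(2)/k_el and add to the k_el row that the log-linear regression uses natural logarithms. Confirm that the reported half-lives satisfy t1/2 × k_el = 0.693.

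The cost is one symbol and one clause in the SAP. No design, data collection or primary analysis changes.

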7 DATA CONVENTIONS

(1) Handling of data for PK assessments

If it is necessary to investigate the data handling because of, for example, a protocol deviation (e.g., the blood collection time fell outside the allowable range, the plasma drug concentration could not be measured, or the blood plasma collection procedures were not followed), the study sponsor will decide on the data handling. PK data that are considered "invalid" will be flagged as such in the data listings and will not be included in the summary tables and figures. These data can be excluded from calculation of PK parameters. The PK data handling will be assessed at the data review meeting prior to database lock and a document for PK data handling will be issued.

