7.1.3.2 Pharmacokinetic Parameters

For the calculation of PK parameters, actual sampling time (in hours rounded to 3 decimal places) relative to dosing should be used. If the sampling was performed before dosing, time after dosing will be set to 0. When k_{el} is missing (or cannot be determined), $t_{1/2}$, $AUC_{0-\infty}$, $AUC\%_{ex}$, CL/F , MRT , V_z/F and V_{ss}/F will not be calculated.

(1) Below the limit of quantification

Concentration below the limit of quantification (BLQ) will be set to 0.

(2) Calculation of AUC

Timepoints with missing concentration data will be ignored. Concentration value at the end time of partial AUC will be calculated by linear-linear trapezoidal rule or by extrapolation using elimination rate constant, if there is no valid data exactly at the time.

(3) Calculation of V_{ss}/F

Pharmacokinetic parameter of V_{ss}/F will be calculated as follows:

$$V_{ss}/F = MRT \times CL/F$$

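### Do the two rules for choosing k_el points, and the optional exclusion of out-of-window samples, leave the NGT/oral comparison open to the analyst's choice?

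*SAP*

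**What the plan says.** **Choice of k_el points (SAP Appendix 1).** The k_el entry first states "The number of data points included in the regression will be determined by visual inspection". It then sets out a search over the last three non-zero points, the last four, and so on, excluding tmax. "The regression with the largest adjusted" R² is selected, and near-ties within 0.0001 go to the fit with more points. The minimum is worded twice: "Wherever possible, a minimum of 3 data points will be used in the estimation of" k_el, and later that k_el "must be positive, and calculated from at least three data points".

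**Out-of-window samples (SAP Section 7 (1)).** Cases where "the blood collection time fell outside the allowable range" are listed among the examples that may make a data-handling decision necessary. The sponsor decides. Data considered invalid are flagged in listings and left out of summary tables and figures. For parameters the wording is permissive: "These data can be excluded from calculation of PK parameters". Decisions are taken at a data review meeting before database lock, and a document is issued. This carries out Protocol 13.3 (1), which gives the sponsor the same decision for window deviations.

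**Time basis.** SAP 7.1.3.2 says "For the calculation of PK parameters, actual sampling time (in hours rounded to 3 decimal places) relative to dosing should be used". Appendix 1 repeats the rule for AUC: "AUC will be calculated using the linear trapezoidal method and actual times".

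**The concern.** Two analysts could read the k_el entry differently. One would choose points by eye and the other would take the largest adjusted R², and they could report different k_el, t1/2 and Vz/F for the same subject. AUC0-∞ also uses k_el, and it is one of the three parameters in the main ANOVA (SAP 8.3.3).

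The sample-exclusion rule looks more serious because it reaches Cmax and AUC0-t. A late sample with a valid assay and a recorded time is usable when parameters are computed at actual times, so dropping it seems needless. Losing the peak sample lowers Cmax. Losing a sample in the decline raises AUC0-t, because missing points are ignored and the trapezoid is linear. The sponsor decides, the study is open-label (Protocol 5.3.1), and no criterion for invalid data is written down. If exclusions fell unevenly on the two routes, the NGT/oral ratio would be biased.

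**Working it through.** The plan states no figure to reproduce here. The check is a reading of the text plus an illustration of size.

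**1. Text on k_el**
- The search is the only complete algorithm in the entry, and it ends in a selection and a binding condition. SAP Section 11 names the software used to calculate the parameters. The natural reading is that the search chooses and a person looks at the plot.
- The two minimum wordings lead to one outcome. Below three points the binding condition fails. SAP 7.1.3.2 says what is not calculated when k_el cannot be determined, and Appendix 1 records zero points in that case.
- Adjusted R², the number of points, and the lower and upper time limits are listed for each subject (SAP 8.3.2, Appendix 1). Any choice by eye can be seen and recomputed.

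**2. Text on late samples**
- The timing deviation triggers a review. It does not define a sample as invalid, and nothing in the SAP requires exclusion.
- Windows are ±1 min at 0.083 h, ±5 min from 0.25 to 12 h and ±15 min from 24 to 48 h (SAP 7.2). Subjects are inpatients from Day -1 to Day 6 (Protocol 8.6.1), which covers every PK sample.
- All concentrations are listed (SAP 8.3.1) and invalid ones are flagged, so parameters can be recalculated with or without a disputed sample.

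**3. Size of the k_el choice**

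From the documents: the 16 sampling times from pre-dose to 48 h (Protocol 9.2.4.1), and for the suspension tmax 0.4–0.8 h and terminal t1/2 5.1–11.8 h (Protocol Section 1 (3)).

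Assumed: C(t) = Σ w_j · ka/(ka − λ_j) · (e^(−λ_j t) − e^(−ka t)), with λ_j = ln 2 / half-life. Half-lives are 0.4 h, 2 h and 5.1, 9 or 11.8 h. Weights are 1/0.08/0.004 or 1/0.15/0.01. ka is 2.6 or 1.9 per h (tmax 0.49–0.61 h). There is no noise.

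| Compared with the last 3 points | 4 points | 5 points |
|---|---|---|
| t1/2 and Vz/F | −11% to −18% | −15% to −25% |
| MRT and Vss/F | at most about −3% | at most about −3% |
| AUC0-∞ | at most −0.2% | at most −0.2% |
| Cmax, AUC0-t | none | none |

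The adjusted R² rule picks 3 points in every one of these profiles. A separate run used other profiles, 10% noise and a quantification limit of 1 or 5 ng/mL, and compared 3, 4 or 5 points with the adjusted R² choice. AUC0-∞ moved by a median of at most 0.3% and by −1.1% to +1.3% at the 5th/95th percentiles. t1/2 moved by a factor of 0.69 to 1.52.

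**4. Size of dropping a sample**

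Same model, terminal t1/2 9 h, ka 2.6, 1.9 or 1.5 per h, log-SD of ka 0.5, 8% residual error. Effects per affected subject:
- Peak sample dropped: Cmax falls by a median of about 6.5–8% (10th–90th percentile roughly 1–18%), and AUC0-t falls by about 2%.
- 4 h sample dropped: AUC0-t rises by about 7.5–11%. This is the worst decline sample, because it leaves a straight line from 2 to 6 h. Dropping the 6, 12 or 24 h sample gives about +1% to +2%.
- Peak sample 6 min late but kept at its actual time: median change 0 to −0.2% in Cmax and −0.2% to −0.5% in AUC0-t.

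**5. Effect on the NGT/oral ratio**

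The ANOVA uses log values from subjects with both treatments. If 3 of 30 completers are affected on one route only, the ratio is multiplied by (1 + change)^(3/30):
- Cmax, typical loss: 0.93^0.1 = 0.993 and 0.92^0.1 = 0.992, a shift of 0.7–0.8%.
- Cmax, 90th-percentile loss of 18%: 0.82^0.1 = 0.980, a shift of 2.0%.
- AUC0-t, 4 h sample: 1.075^0.1 = 1.007 and 1.11^0.1 = 1.010, a shift of 0.7–1.0%.
- Equal losses on both routes: about nil.

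**The case for a change.** The best case for changing the plan is that documenting a decision is not the same as prespecifying its criterion. Listing the number of k_el points does not say which rule chose them. The sponsor makes the exclusion decision in an open-label study, and no text says it is made without sight of route or concentration. The windows are tight, so a deviation could occur. If a subject had only two usable terminal points, the softer minimum would allow a k_el and the stricter one would not. That would decide whether the subject enters the AUC0-∞ ANOVA. The cure would be a few words.

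Part of this stands: the two k_el rules are unranked, and invalid data are not defined. The rest carries less weight. The two-point case is settled by the binding wording, and the grid has eight sampling times from 4 to 48 h. Case review before lock, with a document and flagged listings, is the arrangement Protocol 13.3 (1) calls for. It does not conflict with actual-time calculation, which is needed anyway because in-window samples may be up to 5 or 15 min off. One-sided loss of critical samples is a supposition with no basis in the documents.

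**Conclusion.** No change follows. The k_el wording is a gap that an analyst fills sensibly: run the stated search with at least three points, look at the fit, and list what was used. A different choice by eye could move an individual t1/2 or Vz/F by roughly 11–25%, and by more with noise near the quantification limit. SAP 8.3.3 analyses those parameters only as reference. Cmax and AUC0-t are untouched, and AUC0-∞ changes by about 1% or less in most subjects.

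The exclusion clause permits case review and does not direct that late samples be discarded. An analyst following SAP 7.1.3.2 would keep a validly assayed, timed sample at its actual time, at a cost of about 0.5% or less. Misuse would have to be lopsided by route to matter, and the illustrated imbalance gives a shift of about 1–2%. The plan performs no tests (SAP 6.2) and SAP 8.3.3 sets no acceptance limits, so no formal decision turns on a shift of that size.

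The percentages rest on assumed profile shapes, weights and noise. The documents give only the tmax and half-life ranges and no quantification limit. The conclusion depends mainly on the text: k_el does not enter Cmax or AUC0-t, exclusion is optional, and the choices are visible in the listings.
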